#### **6.4. Subset Analyses**

No subset analyses will be performed.

#### **6.5. Baseline and Other Summaries and Analyses**

##### **6.5.1. Baseline Summaries**

The demographical variables, height, weight, and BMI collected during screening will be summarized. Other data collected at screening that are used for inclusion/exclusion criteria, such as laboratory data, will be considered source data, and will not be required to be reported, unless otherwise noted.

##### **6.5.2. Study Conduct and Participant Disposition**

Participant evaluation groups will show participant disposition by treatment. Frequency counts and percentages will be supplied for participant discontinuation(s) by treatment. Data will be reported in accordance with the sponsor reporting standards.

##### **6.5.3. Concomitant Medications and Nondrug Treatments**

All concomitant medication(s) as well as non-drug treatment(s) will be reported according to current sponsor reporting standards.

#### **6.6. Safety Summaries and Analyses**

See Section [3.2.1](#).

### **7. INTERIM ANALYSES**

*No interim analysis will be conducted for this study.*

#### **7.1. Introduction**

Not applicable

## 7.2. Interim Analyses and Summaries

Not applicable

## APPENDICES

### Appendix 1. Categorical Classes for ECG and Vital Signs of Potential Clinical Concern

#### Categories for QTcF and QTcB

Absolute Maximum (msec)	< 450	$\geq 450$ and $< 480$	$\geq 480$ and $< 500$	$\geq 500$
Maximum Increase from Baseline (msec)	< 30	$\geq 30$ and $< 60$	$\geq 60$	

#### Categories for PR

Absolute Maximum (msec)	$\geq 300$	
Maximum Increase from Baseline (msec)	Baseline $> 200$ and max. increase $\geq 25\%$	Baseline $\leq 200$ and max. increase $\geq 50\%$

#### Categories for QRS

Absolute Maximum (msec)	$\geq 140$
Maximum Increase from Baseline (msec)	max. increase $\geq 50\%$

#### Categories for HR

Absolute Maximum (bpm)	$> 120$
Absolute Minimum (bpm)	$< 40$

#### Categories for Vital Signs

Systolic BP (mm Hg)	min. $< 90$	
Systolic BP (mm Hg) change from baseline	max. decrease $\geq 30$	max. increase $\geq 30$
Diastolic BP (mm Hg)	min. $< 50$	
Diastolic BP (mm Hg) change from baseline	max. decrease $\geq 20$	max. increase $\geq 20$
Supine pulse rate (bpm)	min. $< 40$	max. $> 120$

## Appendix 2. Example SAS Code for MMRM Model

```
proc mixed data=ecg;
  class participant sequence period time treat;
  model qtcf=sequence period baseline time treat time*treat/ddfm=kr;
  repeated time/ subject=period* participant type=cs;
  lsmeans treat*time/cl diff alpha=0.1;
  lsmeans treat*time/cl diff alpha = 0.033;
run;
```

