To increase the confidence that this study has the ability to detect a QTc prolongation in the range of approximately 5 ms, a concurrent positive control will be included to establish assay sensitivity. In this study, moxifloxacin will be used as the active control. Moxifloxacin is a fluoroquinolone antibiotic that produces consistent and predictable QT prolongation and is routinely used as a positive control in TQT studies. Based on recent Pfizer experience from TQT trials conducted at internal CRUs using automated readings, a single 400 mg dose of moxifloxacin produces a maximum mean heart rate-corrected QT interval using Fridericia's correction (QTcF) change from baseline between 7.9 msec and 11.0 msec 2 to 5 hours postdose time points with machine readings. The t_{max} of moxifloxacin is delayed by ≥ 1 hour when administered under fed conditions^{8,9}, with delays in the peak effects on QTc to 4 hours post-dose⁹. Encapsulation of commercially available moxifloxacin tablets to achieve blinding has the potential to have an impact on absorption, therefore encapsulation will not be employed and moxifloxacin will be administered on Day 3 in an open manner. Blood samples from participants randomized to placebo or moxifloxacin will be collected and retained, but will not be routinely analyzed.

All ECG measurements will be performed in triplicate at each nominal sampling time (see [Schedule of Activities](#) and [Electrocardiogram Section 8.3.3](#)). Triplicate measurements are intended to reduce the intrinsic variability and measurement error associated with ECG measurement of the QT/QTc interval. The collection of ECGs at multiple time points is performed to take into consideration the diurnal pattern and variability of QT intervals, dependent upon multiple factors including activity level, postural changes, circadian patterns and food ingestion. The sampling time points have been chosen based on the expected PK profiles of sisunatovir and moxifloxacin. The time to reach maximum concentration (T_{max}) for sisunatovir is approximately 4 to 6 hour postdose based on previous Phase 1 and 2 studies

(Summary of sisunatovir Pharmacokinetics Section 8.5). This schedule will also allow peak QT effects with moxifloxacin, to be captured.⁷

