9.5. Sample Size Determination

A sample size of 42 (7 per sequence) participants will provide approximately 99% power to detect a 5 msec difference between moxifloxacin and placebo at historical moxifloxacin

Tmax (3 hour) to demonstrate the study sensitivity, if the expected mean difference between moxifloxacin and placebo is no less than 10 msec at Tmax.

This calculation used a 1-sided 5% paired t-test and assumed a conservative estimate of common intra-subject standard deviation of 5.61 msec for the change from baseline in QTcF, based on a previous study (C5241001). Previous PCRU TQT studies (A4301023, A3921028, A5761016, A5951151, A5271032, A4251025, A7691017 and B1811062) had an average dropout rate of approximately 2%. Assuming a 2% dropout rate, 41 participants would provide approximately 99% power to demonstrate the study sensitivity.

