#### **5.2.4. Mixed Models Repeated Measures (MMRM) Analysis**

*Change from baseline in QTcF intervals will be analyzed using a MMRM model with sequence, period, treatment, time (post-dose timepoint) and treatment by time interaction as fixed effects, participants as a random effect, and baseline QTcF as the covariate. A compound symmetry covariance matrix will be fitted to the repeated times within participant (other covariance matrices will be considered if necessary), and the Kenward-Roger approximation will be used for estimating degrees of freedom. The ECG analysis set will be used for the MMRM analysis.*

Standard SAS output will be provided to support the statistical summary table for the analysis model, but will not be included in the CSR.

Example SAS code is provided in [Appendix 2](#).

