##### 6.1.1.2. Sensitivity/Supplementary Analyses

By time analysis (intersection-union test) will be provided as the supplementary analyses. Briefly, change from baseline in QTcF will be analyzed by MMRM as described in Section 5.2.4 using ECG analysis set. All planned post-dose time points on Day 3 and 4 of each period will be included in the model. The least-squares (LS) means of change from baseline QTcF of sisunatovir and placebo, as well as the  $\Delta\Delta\text{QTcF}$ , 5.2.1 and the corresponding 90% CIs will be reported for each post-dose timepoint. The LS means and 90% CI of  $\Delta\Delta\text{QTcF}$  (Y-axis) will be plotted against time post dose (X-axis).

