### **6.2.2. Baseline adjusted QTcF of moxifloxacin and placebo at Tmax of 3, 4, and 5 hours on Day 3.**

Change from baseline in QTcF will be analyzed by MMRM as described in Section 5.2.4 using ECG analysis set. All planned post-dose time points on Day 3 and 4 of each period will be included in the model. The least-squares (LS) means of change from baseline QTcF of moxifloxacin and placebo, as well as the difference between moxifloxacin and placebo, and the corresponding 90% CIs will be reported for each post-dose timepoint. The 96.7% CIs for mean differences between moxifloxacin and placebo at 3, 4, and 5-hr pose-dose will also be provided as the Bonferroni-adjusted two-sided 90% CIs.

A visualization displaying the model predicted mean difference in change from baseline QTcF between moxifloxacin and placebo and the corresponding 90% CIs will also be created.

*The study will be deemed adequately sensitive to detect QT/QTc prolongation if any of the lower limits of the two-sided Bonferroni-adjusted 90% CI (96.7% CI) for mean differences between moxifloxacin and placebo at any of the 3, 4 and 5-hr pose-dose, respectively, are greater than 5 msec.*

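### The SAP's example MMRM code leaves out the participant random effect that the text specifies, so as printed it overstates the standard errors behind the assay-sensitivity test and the by-time intervals

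*SAP*

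**What the plan says.** SAP section 5.2.4 describes a model for change from baseline in QTcF with sequence, period, treatment, time and "treatment by time interaction as fixed effects, participants as a random effect, and baseline QTcF as the covariate". It adds: "A compound symmetry covariance matrix will be fitted to the repeated times within participant". Protocol section 9.3.3 gives the same specification, and SAP section 2.1 declares no departure from the protocol.

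Section 5.2.4 then points to Appendix 2 for example code. The MODEL statement there lists sequence, period, baseline, time, treatment and time-by-treatment. There is no RANDOM statement. Participant enters only through the REPEATED statement: "repeated time/ subject=period* participant type=cs".

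Two analyses use this model:

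- **Assay sensitivity (SAP 6.2.2).** The rule is pass or fail: "The study will be deemed adequately sensitive to detect QT/QTc prolongation if any of the lower limits of the two-sided Bonferroni-adjusted 90% CI", that is the 96.7% interval at 3, 4 or 5 h, lies above 5 msec.
- **Supplementary by-time analysis of sisunatovir (SAP 6.1.1.2).** Here "change from baseline in QTcF will be analyzed by MMRM as described in Section 5.2.4 using ECG analysis set".

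The sample size in protocol section 9.5 rests on a within-participant comparison: "This calculation used a 1-sided 5% paired t-test and assumed a conservative estimate of common intra-subject standard deviation of 5.61 msec".

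**The concern.** In PROC MIXED, different levels of the REPEATED subject are independent blocks. With period-by-participant as the subject and no RANDOM statement, one participant's sisunatovir, placebo and moxifloxacin periods are modelled as if they came from three unrelated people. In a crossover, a participant's own tendency to show a larger or smaller QTcF change cancels from the treatment difference. The printed code does not let it cancel in the standard error.

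The estimated difference is as precise as it should be, but the interval around it is too wide whenever participants differ in mean change. Moxifloxacin could then miss the 5 msec threshold because of a modelling omission, which would undermine a negative QT result for sisunatovir. The by-time upper limits for sisunatovir would be too high for the same reason.

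**Working it through.** **Inputs from the documents.** 42 participants, or 41 after 2% dropout; within-participant SD of QTcF change 5.61 msec; expected moxifloxacin-placebo difference 10 msec; sizing test one-sided 5% paired t (all protocol 9.5). Threshold 5 msec, one-sided 0.05/3 at each of 3, 4 and 5 h (protocol 9.1.2, SAP 5.1.2).

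**Assumed.** The between-participant SD of QTcF change left after the sequence and baseline terms, written sb. The documents do not give it; I use 0, 2, 4 and 5.61 msec.

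**1. The plan's own figure.** SE of the paired difference = √(2 × 5.61² / 42) = 1.224 msec. With a margin of 10 − 5 = 5 msec and one-sided alpha 0.05, the noncentral t gives 99.1% power for n = 42 and 99.0% for n = 41. The stated 99% reproduces, and it relies on the participant effect cancelling.

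**2. Reported SE under each model.** In the balanced crossover, at one time point:

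- with the participant random effect: √(2 × 5.61² / n), whatever sb is;
- as printed: √(2 × (5.61² + sb²) / n).

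The ratio is √(1 + sb²/5.61²). The sampling SD of the estimate is the first expression in both cases. For n = 42, with half-width = t(0.05/3, 80 df) = 2.165 times the SE:

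| sb (msec) | 5.61² + sb² | Reported SE, as printed | Excess | 96.7% half-width |
|---|---|---|---|---|
| 0 | 31.47 | 1.22 | 0% | 2.65 |
| 2 | 35.47 | 1.30 | 6% | 2.81 |
| 4 | 47.47 | 1.50 | 23% | 3.26 |
| 5.61 | 62.94 | 1.73 | 41% | 3.75 |

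With the random effect, every row would read 1.22 and 2.65.

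**3. Power at a single time point, as printed.** Power = Φ((d − 5 − t × reported SE) / sampling SD), with n = 41, sampling SD 1.239 and 80 df.

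| True difference d | sb = 0 | 2 | 4 | 5.61 |
|---|---|---|---|---|
| 10 msec | 97% | 96% | 92% | 84% |
| 7.9 msec | 57% | 52% | 38% | 24% |

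**4. Power under the actual any-of-three rule, as printed.** 400,000 trivariate normal draws per setting, n = 41, correlation between times 0.3 to 0.7 (assumed), 120 df. The sb = 0 column is also what the corrected model gives at any sb, apart from small differences in degrees of freedom.

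| True effect at 3/4/5 h (msec) | sb = 0 | 2 | 4 | 5.61 |
|---|---|---|---|---|
| 10/10/10 | 99–100% | 99–100% | 98–99% | 94–98% |
| 8/10/8 | 97–99% | 96–98% | 92–95% | 84–88% |
| 7.9/7.9/7.9 | 76–86% | 71–82% | 57–68% | 40–50% |

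The 7.9 msec figure is the low end of the range in protocol section 4.2, "change from baseline between 7.9 msec and 11.0 msec 2 to 5 hours postdose time points". It is a change from baseline and not a placebo-corrected difference, so it serves only as an illustration.

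**5. Check by fitting both models.** REML simulation, 1,000 replicates per setting: 42 participants, 3 periods, 9 times, period-specific baseline covariate, within-participant variance split equally between the participant-by-period and residual parts (assumed), effect 8/10/8 msec.

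| | sb = 0 | 2 | 4 | 5.61 |
|---|---|---|---|---|
| Printed code: mean reported SE | 1.22 | 1.29 | 1.48 | 1.69 |
| Printed code: empirical SD of the estimate | 1.26 | 1.24 | 1.24 | 1.24 |
| Printed code: pass rate | 98% | 98% | 95% | 88% |
| With participant effect: mean reported SE | 1.21 | 1.22 | 1.22 | 1.22 |
| With participant effect: pass rate | 98% | 99% | 99% | 99% |

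The fitted models agree with the closed form to within a few hundredths of a millisecond. The printed response is QTcF and not its change from baseline, but that does not alter the treatment differences because baseline is a covariate.

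**The case against.** The strongest reply is that the specification is already right. Both documents name the participant random effect, the analysis sections refer to section 5.2.4 and not to the code, and the code is labelled an example. The text supplies the random effect and the code supplies the block, so a careful programmer could reach the intended model. That is true, and it limits the point to a text-code mismatch. It does not remove it: this is the only implementation given, section 5.2.4 refers to it, and it carries this study's alpha levels. The allowance for other covariance matrices if necessary states no criterion, and in a sponsor-open study the choice should not wait for data.

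The second reply concerns size, and much of it stands. No between-participant SD is given. The response is a change from a nine-ECG, period-specific baseline that is also a covariate, so differences in QTcF level are largely removed and sb could be small. Values of 4 and 5.61 msec put 16/47.47 = 34% and 50% of the variance of change between participants, and nothing in the documents supports or excludes that. The protocol also calls 5.61 msec conservative, and the single-time figures are not the decision rule. Under that rule and the 10 msec planning premise, power stays at 92% or more for sb up to 4 msec in both profiles that reach 10 msec.

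Third, the consequences are bounded. The error is conservative, the by-time sisunatovir analysis is supplementary, and the primary decision rule is not formally conditional on assay sensitivity. All of this stands.

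**Conclusion.** The concern holds. The printed code does not fit the model that the SAP and protocol specify, and it overstates the standard error of each treatment contrast by the factor √(1 + sb²/5.61²). The mismatch and its direction are certain. The size depends on a between-participant SD that the documents do not report, and the range includes zero.

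The loss is negligible if that SD is small or the moxifloxacin effect is a sustained 10 msec. It becomes material if the SD is about 4 msec or more and the effect is peaked or near the low end of the historical range. The risk is a false failure of the positive control and over-wide by-time intervals. It is not a false claim of sensitivity or of no QTc effect. The primary concentration-QTc model has its own participant random effects and is untouched. This should be fixed because the intervals are wrong in a pass/fail analysis and the correction is trivial.

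**What to change.** In SAP Appendix 2, add `random participant;` and keep the existing REPEATED statement. In SAP section 5.2.4, add one sentence saying that compound symmetry applies to the times within each participant-by-period, in addition to the participant random effect. The same clarification in protocol section 9.3.3 would keep the documents aligned but is optional, since protocol section 9 leaves further detail to the SAP. Make the change before database release.

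The cost is one line of code and one sentence, with no new data. In simulation with no between-participant variance, the added term cost nothing: the pass rate was 97.9% with or without it.

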### Appendix 3. List of Abbreviations

Abbreviation	Term
Abs	Absolute
AE	adverse event
AUC	area under the curve
AUC 12	area under the curve from time 0 to 12 hours
AUC 24	area under the curve from time 0 to 24 hours
BLQ	below the limit of quantitation
BP	blood pressure
BPM	beats per minute
B/P	blood to plasma
CI	confidence interval
C max	maximum observed concentration
C-QT	concentration QT
CRU	clinical research unit
CSR	clinical study report
CV	coefficient of variation
ECG	electrocardiogram
HR	heart rate
ICH	International Council for Harmonisation
LLOQ	lower limit of quantitation
LS	least-squares
LSM	least-squares mean
MAR	missing at random
Min	minute
MMRM	mixed-effects model with repeated measures
Msec	millisecond
N/A	not applicable
ND	not done

Abbreviation	Term
NS	no sample
PD	pharmacodynamic(s)
PK	pharmacokinetic(s)
PR	PR interval
PT	preferred term
Q&As	questions and answers
Q-Q	quantile-quantile
QRS	QRS complex
QTc	corrected QT
QTcB	corrected QT (Bazett's method)
QTcF	corrected QT (Fridericia method)
RR	RR interval
SAE	serious adverse event
SAP	statistical analysis plan
SD	standard deviation
Sec	second
SoA	schedule of activities
TEAE	treatment-emergent adverse event
TQT	thorough QT
T max	time for maximum observed concentration
